- Review past medical history in Armed Forces Health Longitudinal Technology Application (AHLTA) to verify the inclusion/exclusion criteria including previous encounter, vital signs review, medication list, co-morbidities, demographics, problems list, and note any prior acupuncture received. (research only)
- Record: Date of birth, age, gender, race, ethnicity, last 4 of social security number, name of standard of care rescue medications (over-the-counter and prescription), current email address (to be used for scheduling only), height (in

inches), weight (in pounds), history of traumatic brain injury, concussion, or any mild to severe head trauma, medication use, history of acupuncture. (research only)

- We will ask what the subjects expectations are regarding acupuncture's effectiveness for migraine. (research only)
- We will instruct subjects not to take their over-the-counter and prescription headache medications until after their visit with the research staff. (Standard care)
- We will instruct subjects to bring their over-the-counter and prescription headache medications with them to each visit if their symptoms do not resolve from the acupuncture treatment. (research only)
- Patient will be instructed to contact the Research Coordinator, as soon as possible, after onset of migraine symptoms (including prodromal symptoms) to schedule an emergent visit with the research staff. (research only)
- Patient will be given a contact card with the names and phone numbers of the research staff to contact when they have a migraine episode.

Migraine Episode:

- Self-reported headache pain severity (0=no headache, 1=mild, 2=moderate, 3=severe) (Standard care)
- Record type and amount of rescue medications (over-the-counter and prescription) use in the past 7 days. (research only)
- Acupuncture treatments will be subject dependent, and points could include the N point (on scalp); various auricular points to include Shen Men, Point Zero, thalamus and Omega-2; body points to include Liver 2, Liver 3, Gall Bladder 20, bladder 10; and surface release over tense areas in the neck or shoulders. (Standard care)
- Researchers will document the points used. (Standard care)
*If after 20-30 minutes these patients have not had resolution of their headache, they may take their standard of care rescue medication. (research only)
- The subject will sit for 20-30 minutes post-acupuncture(research only), and then the needles will be removed and the subject will be asked:
 - Self-reported headache pain severity (0=no headache, 1=mild, 2=moderate, 3=severe) (research only)
- Subject is allowed to leave and will be informed of the following telephone follow ups:
- 2 Hours post acupuncture:
 - Self-reported headache pain severity (0=no headache, 1=mild, 2=moderate, 3=severe) (research only)
- 4 Hours post acupuncture:
 - Self-reported headache pain severity (0=no headache, 1=mild, 2=moderate, 3=severe) (research only)
- 24 Hours post acupuncture:
 - Self-reported headache pain severity (0=no headache, 1=mild, 2=moderate, 3=severe)
 - Would you use acupuncture for future pain management? (Yes or no)
 - Would you prefer acupuncture or your rescue meds (both over-the-counter and prescription) for future episodes?
 - Record type and amount of rescue medications (over-the-counter and prescription) used since acupuncture. (research only)

Patients with missed phone calls will not be withdrawn from the study. If there is a missed call, we will mark as 'missed', including the reason and continue with the next phone call.

The Research Coordinator will record the name of the AI performing the acupuncture and also the placement of the acupuncture needles for each migraine episode.

Placement of Acupuncture:

[figure not shown]
Acupuncture treatments will be subject dependent, and points could include the N point (on scalp) (Figure 1); various auricular points to include Shen Men(Figure 2), Point Zero(Figure 3), thalamus(Figure 4) and Omega-2(Figure 5); body points to include Liver 2(Figure 6), Liver 3(Figure 6), Gall Bladder 20(Figure 7), bladder 10(Figure 7); and surface release over tense areas in the neck or shoulders. We will utilize the Seirin J-Type Acupuncture needles (Figure 98). Intermittent placement checks by the medical acupuncturist will be performed.

This study will follow all FDA requirements for the safe use of these devices.

Only the investigators listed on this study will perform the insertion of the acupuncture needles. All investigators are trained in this acupuncture technique and credentialed by the Credentials committees.

The Food and Drug Administration (FDA) regulates acupuncture needles as a class II medical device, because they are intended for use in the cure, mitigation, treatment, or prevention of disease in man or are intended to affect the structure or function of the body of man. The FDA regulates the acupuncture needles (see 21 CFR 880.5580), but not the practice of acupuncture itself.

The needles being used are Seirin J-Type Acupuncture needles (Figure 8), which are exempt from premarket notification by the FDA for use in acupuncture and will be used in accordance with their FDA approved labeling.

3.6.1. Interventions, Observations, or Data Sought:

We will measure subject’s migraine pain level, doses of analgesics taken before intervention and at 20-30 minutes, 2 hours, 4 hours, and 24 hours post treatment. Additionally, we will measure patient centered outcomes and receptivity to acupuncture. Acupuncture treatments will be subject dependent, and points could include the N point (on scalp); various auricular points to include Shen Men, Point Zero, thalamus and Omega-2; body points to include Liver 2, Liver 3, Gall Bladder 20, bladder 10; and surface release over tense areas in the neck or shoulders. Researchers will document the points used, and data will be aggregated to determine overall effectiveness. Sub-group analysis by points will be performed to determine if there is more usefulness in 1 point or combination of points.

3.6.2. Data Collection and Processing:

Data will be collected and recorded in a spreadsheet. At the conclusion of the study, all personally identifying information will be removed prior to analysis.

3.6.3. Setting:

Male and female (DoD beneficiaries). Age 18 years or older, who currently take rescue medication to treat their acute migraine episodes at the Mike O’Callaghan Federal Medical Center (MOFMC).

3.6.4. Date(s):

August 2015 through August 2017

3.6.5. Source of Research Material:

Source of Research Material per Migraine (Procedures)	# Routine Care	# Research Driven	# Total Procedures
Medical Record Review	0	1	1
Acupuncture	6	0	6
Questions: Pain Severity	12	18	30
Questions: Acupuncture for future pain management	0	6	6
Questions: Preference of acupuncture vs rescue meds	0	6	6
Questions: Rescue medication usage	0	12	12

3.6.6. Subjects:

Male and female (DoD beneficiaries). Age 18 years or older, who currently take rescue medication to treat their acute migraine episodes at the Mike O’Callaghan Federal Medical Center (MOFMC). No other special populations (e.g., children, military basic trainees, prisoners, detainees) will be recruited.

3.6.7. Inclusion/Exclusion Criteria:

Inclusion:

- Male and female DoD beneficiaries, age 18 years or older, who have been previously prescribed rescue medication to treat their acute migraine episodes.

Exclusion:

- Pregnant
- Absence of ear
- Active cellulitis of ear
- Ear anatomy precluding identification of acupuncture landmarks
- Use of Hearing Aids that preclude the insertion of needles
- Use of anticoagulants
- Unable to drive during rapid onset of migraine or inability to find someone to drive you

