This will be an exploratory observational trial of rescue acupuncture for the treatment of acute migraine in military beneficiaries to gain information to inform the power analysis of a larger, more definitive trial. We do not seek to definitively answer the question of whether this acupuncture protocol is effective; rather, we seek to estimate the proportion of migraine episodes that result in headache-free status 20-30 minutes, 2 hours, 4 hours, and 24 hours after an acupuncture treatment. Acupuncture treatments will be subject dependent, and points could include the N point (on scalp); various auricular points to include Shen Men, Point Zero, thalamus and Omega-2; body points to include Liver 2, Liver 3, Gall Bladder 20, bladder 10; and surface release over tense areas in the neck or shoulders. Researchers will document the points used, and data will be aggregated to determine overall effectiveness. Sub-group analysis by points will be performed to determine if there is more usefulness in 1 point or combination of points. These estimates will inform statistical power calculations for a future randomized controlled trial (RCT) that directly compares the effectiveness of Rescue Acupuncture with medical management of acute migraine with rescue medication. We will also assess the feasibility of this study protocol as well as patient receptivity and satisfaction.

5. Subjects:

Male and female DoD beneficiaries ages 18 years or older will be recruited at the Mike O’Callaghan Federal Medical Center (MOFMC). No special populations (e.g., pregnant women, children, military basic trainees, prisoners, detainees) will be recruited.

6. Inclusion/exclusion criteria:

Inclusion:

- Male and female DoD beneficiaries, age 18 years or older, who have been previously prescribed rescue medication to treat their acute migraine episodes.

Exclusion:

- Pregnant
- Absence of ear
- Active cellulitis of ear
- Ear anatomy precluding identification of acupuncture landmarks
- Use of Hearing Aids that preclude the insertion of needles

- Use of anticoagulants
- Unable to drive during rapid onset of migraine or inability to find someone to drive you

7. Number of Subjects: TOTAL NUMBER OF SUBJECTS (nation-wide/study-wide): 60

8. Use of an Investigational New Drug: N/A

9. Use of an Investigational Device: Seirin J-Type Acupuncture needles and Sedatelec ASP Original Gold Acupuncture needles, 510(k) exempt as Class II device under 21 CFR 880.5580

10. Use of a Placebo: N/A

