We will estimate the magnitude of effect that acupuncture has as an alternative to medication for treatment of acute migraine, as measured by change in headache pain severity 20-30 minutes, 2 hours, 4 hours, and 24 hours post treatment.

3.3. Significance:

Proof that acupuncture is superior to medication for treatment of migraine in military beneficiaries would result in less lost duty days, decreased medication use, and improved quality of life.

3.4. Military Relevance:

Migraine headaches are common in deployed US Army soldiers and exceed the expected prevalence. These headaches result in impaired duty performance and are a frequent cause of sick call visits. Migraine headaches tend to persist after deployment in many soldiers.⁶ A survey of a cohort of returning US Army Iraqi war veterans revealed that Soldiers with migraine made a total of 490 sick call visits for headache over a 3-month period of which 90 were for possible migraine. In all, 75% of the soldiers with migraine used over-the-counter analgesics and only 4% used triptans. Soldiers with migraine contacted 3 months after returning from Iraq had a mean of 5.3 headache days per month and 36% had a Migraine Disability Assessment Scale grade of 3 or 4.

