Acupuncture is a nonpharmacologic treatment approach that has been proven to significantly reduce the frequency and severity of episodic migraines.^{6,7} However, there is (to our knowledge) only one published randomized controlled trial that evaluated the efficacy of acupuncture relative to a rescue medication for the acute treatment of migraine.⁸ This represents a significant research and knowledge gap. We propose to fill this gap by conducting a large, carefully designed, phase III, randomized controlled trial that directly compares the efficacy of acupuncture with rescue medications in the acute treatment of episodic migraine.

The needles being used are Seirin No. 3(0.20)x30mm stainless steel J-type with tube acupuncture needles which are approved by the FDA for use in acupuncture and will be used in accordance with their FDA approved labeling. As part of this study, the acupuncture needles themselves are not the object of the investigation, the process of acupuncture and the effect it has is what we are studying. The needles are merely the avenue we use to perform the acupuncture. According to 21 CFR 880.5580, an acupuncture needle is a device intended to pierce the skin in the practice of acupuncture.⁹ There are no known restrictions on the use of the acupuncture needles that prevent them from being used by qualified practitioners of acupuncture as they deem appropriate.

3.5.1. Bibliography:

1. Headache Classification Committee of the International Headache Society. The International Classification of Headache Disorders, 3rd edition (beta version). *Cephalalgia*. 2013; 33(9):629-80.
4. Silberstein SD. Practice parameter: evidence-based guidelines for migraine headache (an evidence-based review): report of the Quality Standards Subcommittee of the American Academy of Neurology.[Erratum appears in *Neurology* 2000 Jan 9;56(1):142]. *Neurology*. 2000;55(6):754-762.

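### No listed item records migraine features at a treated episode or headache frequency at screening, so the resolved proportion cannot be reported for confirmed or episodic migraine

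*Combined protocol and SAP*

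**What the plan says.** **Entry.** Sections 3.6.7 and 6 (Protocol Summary) admit adults "who have been previously prescribed rescue medication to treat their acute migraine episodes". Sections 3.6.3 and 3.6.6 speak instead of current use of such medication. No listed exclusion concerns chronic migraine or another headache disorder. The Screening Visit in 3.6 uses the medical record "to verify the inclusion/exclusion criteria including previous encounter, vital signs review, medication list, co-morbidities, demographics, problems list".

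**Episode.** The subject is told to make contact "as soon as possible, after onset of migraine symptoms (including prodromal symptoms) to schedule an emergent visit with the research staff". At the visit, staff record a 0-to-3 pain score, rescue medication over the past 7 days and the points used.

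**Target quantity.** Section 4 of the Protocol Summary states: "we seek to estimate the proportion of migraine episodes that result in headache-free status". It adds that the estimates will feed the power calculation of a randomised trial, described there as a comparison in acute migraine. Section 3.5 describes a proposed randomised trial that "directly compares the efficacy of acupuncture with rescue medications in the acute treatment of episodic migraine", having just separated episodic from chronic migraine by how often attacks occur.

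**The concern.** The primary quantity has migraine episodes as its denominator, so what counts as one decides what is estimated. Here that rests on a past prescription and the subject's own judgement on the day. Section 3.5 characterises migraine by nausea, vomiting and other neurologic symptoms and cites a headache classification (reference 1), but the methods use neither.

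The study exists to supply a response rate for a later trial. If some treated headaches are not migraine, or some subjects have chronic migraine, and these respond differently, the rate handed on belongs to a mixture. More subjects or episodes would not correct that. Features not recorded at the time of the attack cannot be reliably recovered later.

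**Working it through.** **1. Is there a figure to reproduce?** No. Sections 6.2 and 6.4 give 60 enrolled and 30 completing, with up to 6 episodes each (at most 30 × 6 = 180). They state no expected response, precision or power. Section 6.3 is descriptive.

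**2. Are the classifying data collected?**

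| Needed | Where it would be | What is listed |
|---|---|---|
| Migraine features at the episode | 3.6, Migraine Episode; 3.6.5 table | Pain score, rescue use, points. The table's question types are severity, future use, preference and rescue use |
| Headache or migraine days per month | 3.6, Screening Visit | Demographics, rescue drug names, head-trauma history, acupuncture history, expectations; no frequency |
| Symptoms other than head pain (a secondary outcome in 6.1) | Episode visit and the 2, 4 and 24 hour calls | Not listed at any of them |

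The nearest substitutes do not fill the gap. Seven-day rescue use is not a count of headache days. Treated episodes are capped at six, so they do not measure attack frequency. Head-trauma history is not migraine type.

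**3. Size of a possible shift (all rates assumed).** Let f be the share of treated episodes outside the target, p_m the response in target migraine and p_o the response in the rest.

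p_obs = (1 − f) × p_m + f × p_o, so the shift is f × (p_o − p_m).

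Take p_m = 30%. The extremes are 0.3 × (20% − 30%) = −3 points and 0.3 × (70% − 30%) = +12 points.

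**4. Consequence for the later trial.** Assume a comparator response of 15%, two-sided 5% level, 80% power, and the usual two-proportion formula with pooled variance under the null. The size needed at 30% versus 15% is 121 per arm. True power is computed at 30% versus 15% with the planned size.

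| p_o | f | p_obs | Planned per arm | True power |
|---|---|---|---|---|
| 50% | 10% | 32% | 97 | 71% |
| 50% | 20% | 34% | 80 | 62% |
| 50% | 30% | 36% | 67 | 55% |
| 20% | 10% | 29% | 137 | 85% |
| 20% | 20% | 28% | 156 | 89% |
| 20% | 30% | 27% | 180 | 93% |

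The later trial could be too small or too large, and the plan gives no means of telling which.

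**5. Counting by episode can add weight.** Suppose 5 of 30 subjects (17%) have chronic migraine and use all six treatments: 5 × 6 = 30 episodes. Give the other 25 the trainee rates in section 3.4. At 0.70 per month they contribute 25 × 0.70 × 3 = 52.5 episodes, and chronic subjects supply 30/82.5 = 36% of the total. At 1.4 per month they contribute 105, and the share is 30/135 = 22%. The 5 subjects are an assumption.

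**6. Against sampling error.** At p = 30% the 95% half-width is 1.96 × √(0.21/n). It is 16.4 points for 30 episodes and 6.7 for 180 independent ones. With an assumed within-subject correlation of 0.3, the effective number is 180/(1 + 5 × 0.3) = 72 and the half-width 10.6. Most shifts in the illustration lie inside that error, but unlike it they do not shrink as episodes accumulate.

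**The case against.** **What stands.** Entry is not unchecked. A migraine prescription verified against encounters, medication list and problem list is indirect evidence of a clinician-treated migraine history. Subjects are asked to call for migraine symptoms, not for any headache. The study is exploratory and tests no hypothesis, and entry by treated migraine is a defensible pragmatic choice. Because subjects may call in the prodrome, restricting the main proportion to feature-positive episodes could drop early-treated attacks. That is a reason to add strata rather than redefine the main row. None of this confirms the individual episode or the subtype.

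**What a reader might infer, and should not.**

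- Section 3.4 reports "490 sick call visits for headache over a 3-month period of which 90 were for possible migraine". One might conclude that about 82% of headaches in people with migraine are something else. The text does not classify the other 400 visits, and the separate cadet study described in 3.4 treats definite and possible migraine as different categories. These were also sick-call visits for headache by soldiers, not calls for migraine by patients with a prescription. The figure gives no contamination rate for this study.
- One might count chronic migraine as a built-in failure. Section 3.4 says that migraine after brain injury is refractory to medication, not to acupuncture, and suggests acupuncture as an adjunct.
- One might say the study misses the later trial's population outright. Only section 3.5 says episodic. Section 4 of the Protocol Summary says acute migraine, and the later trial's eligibility rules are not given.

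**Conclusion.** The gap is confirmed. No listed item records migraine features at the episode or headache frequency at screening, so the resolved proportion can mix headache types and cannot be split into episodic and chronic migraine. The documents do not show that mixing will be large, or which way it would act. The range of −3 to +12 points and the planned sizes above rest entirely on assumed response rates, shares and comparator. The finding also assumes that no data form outside the document adds these items. It is a cheap improvement to an exploratory study, not a flaw that invalidates it.

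**What to change.** 1. **Screening Visit (3.6).** Record headache days and migraine days per month, and classify each subject as episodic or chronic by a stated rule.
2. **Migraine Episode visit (3.6).** Before needling, add a short yes/no list of migraine features, such as those section 3.5 names (nausea, vomiting, other neurologic symptoms), and note whether the subject is still in the prodrome. This also gives a baseline for the secondary outcome on other symptoms. Measuring change would need the same items at the follow-up calls.
3. **Statistical Analysis (6.3).** Keep all treated episodes as the main row. Show beside it the proportion in feature-confirmed episodes and, separately, in episodic and chronic subjects. State that episodes treated in the prodrome may not yet show features.
4. **Reconcile** section 3.5 with section 4 of the Protocol Summary on whether the later trial concerns episodic migraine or all acute migraine.

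Eligibility and treatment do not change. The cost is about a minute of questions per visit, a few fields in the spreadsheet, and strata that will be small and imprecise with 30 subjects.

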3.6.8. Instrumentation: N/A

4.0. Human Subject Protection:

4.1. Recruitment:

All potentially eligible patients will be offered an opportunity to participate. PCM referrals and posted advertisements will be utilized for recruiting subjects to the study. Some patients may be patients of the PI or AI, however, they will have the study staff recruit their patients to prevent any misconception of coercion or undue influence. When a potential subject is identified by the treating PCM, the patient will either be provided a contact number to the Research Staff, the Research Staff will be given the potential subjects contact information by the PCM, or the PCM will come and get the Research Staff to speak with the patient directly.

4.2. Consent Processes:

Informed Consent and HIPAA authorization will be sought in advance from each prospective subject and appropriately documented in accordance with 32 CFR 219.117. Potential candidates will be notified about the study either through posted advertisements or by their care provider and will be given the opportunity to consent by one of the referred study coordinators. The study coordinator will provide a written copy of the Informed Consent Document (ICD). The subject may decline to consent without prejudice. At the subjects' discretion, they may take the ICD home to discuss further prior to making a decision. If the subject consents, a copy of the ICD will be given to the subject. No vulnerable populations are included in this research study. Subjects who cannot provide Informed Consent will not be allowed to participate. No Legally Authorized Representatives (LAR) will be utilized. Each subject will be asked to place their study-related PHI/PII into the "Nellis Acupuncture Research Data Repository (FWH20140048H)" for future research. If the subject does not give their authorization, then all PHI/PII will be destroyed no later than at the closure of the study.

4.3 Participation Compensation:

Subjects will not be paid for participation in this study.

